10.1.4 Clinician and self-rating scales

Clinician and patient self-rating scales will be recorded in the CRF. Observed values and changes from baseline in relationship to both first and most recent implant will be listed for each study time point at which these data are recorded. For continuous or discrete outcomes, observed values and changes from baseline will be summarized at each time point. Nominal outcomes will be categorized and summarized as frequencies and percentages of subjects at each time point. Each rating scale to be evaluated is described below.

10.1.4.1 *Global Clinical Assessment (GCA)*

The GCA is done by the clinician and measures patient clinical status via a visual analog scale (VAS). GCA will be reported as the distance from the left endpoint to the clinician's mark divided by the total length of the horizontal line being marked.

10.1.4.2 *Activities of daily living (ADL) rating / Karnofsky performance status (KPS) scale*

ADL / KPS is a self-rated scale that measures the patient's ability to perform daily functions, ranging from 0 ("dead") to 100 ("normal, no complaints, no evidence of disease").

10.1.4.3 *Quality of life scale / EORTC QLQ-C30*

Quality of life will be assessed using the European Organisation for Research and Treatment in Cancer (EORTC) Quality of Life Questionnaire (QLQ)-C30 version 3.0 ([Aaronson et al. 1993](#)) which uses discretely-scaled responses to 30 questions to derive global health status / quality of life, functionality and symptom scales. The raw data will be used to calculate the derived scales using the EORTC QLQ-C30 Scoring Manual ([Fayers et al. 2001](#)). Per the manual, any derived scale for which more than half of the individual questions that comprise the scale are missing will be set to missing; otherwise, missing values will be ignored (which has the same effect as imputing the average response among non-missing questions that comprise the scale).

10.1.4.4 *Pain scale*

Subjects will be asked to rate their pain on a discrete scale (from 0 = "no pain" to 10 = "worst pain imaginable, unbearable"). Specific anatomical locations of pain will also be recorded.

10.1.4.5 *Eastern Cooperative Oncology Group (ECOG) performance status*

The ECOG Performance Status is used by clinicians to assess disease progression and how the disease is affecting the daily living abilities of the patient; it is scaled as follows:

Status	Description
0	Fully active, able to carry on all pre-disease performance without restriction
1	Restricted in physically strenuous activity but ambulatory and able to carry out work of a light or sedentary nature, e.g., light house work, office work
2	Ambulatory and capable of all self-care but unable to carry out any work activities. Up and about more than 50% of waking hours
3	Capable of only limited self-care, confined to bed or chair more than 50% of waking hours

Status	Description
4	Completely disabled. Cannot carry on any self-care. Totally confined to bed or chair
5	Dead

10.2 Statistical Analysis Methods

- All statistical testing will be considered strictly exploratory as the study was not powered based on statistical considerations.
- Exact 95% CIs will be calculated for rates.
- Survival analysis methods will be used analyze time-to-event outcomes; for non-mortality outcomes, the term “survival” will still be used to describe non-occurrence of the event being analyzed. Kaplan-Meier plots with 95% CIs will be generated to show probability of survival as a function of time since implantation. In addition, Kaplan-Meier estimates of the median survival time will be reported.
- The relationship between times from diagnosis of Stage IV disease diagnosis to the primary analysis time of origin and primary analysis time of origin to death will be examined (if feasible) using Cox regression model and Kaplan-Meier curves.
- The relationship between time-to-event outcomes and tumor markers (and other covariates, if feasible) will be assessed using Cox regression. Kaplan-Meier plots will be produced for descriptive assessment.
- Survival comparisons by implantation number will be performed, if feasible.
- Other explorations of efficacy data may be performed (if feasible), such as:
 - Testing for effects of baseline values of tumor markers and presenting stratified descriptive statistics, if deemed appropriate.
 - Plotting chronological subject profiles of specific parameters; i.e., plotting a set of parameters over time on the same graph for a given subject.

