10 EFFICACY ANALYSES

Efficacy parameters will be listed and summarized for all implanted subjects, stratified by cancer type. There will be no formal hypothesis testing and no group comparisons are currently planned. The primary efficacy outcome will be all-cause mortality, as defined above in [Section 3.3.1](#).

Secondary efficacy outcomes will be:

- Time from first implantation to death
- Time from diagnosis of Stage IV disease to death
- Changes from baseline based on MRI, CT or PET-CT scan, and other appropriate imaging techniques (e.g., sonography, bone scans, other x-rays) as indicated, if feasible.
 - In primary and/or secondary tumor size (volume, area) and
 - In state (necrosis, vascularization) on MRI, CT or PET-CT scan, and other appropriate imaging techniques (e.g., sonography, bone scans, other x-rays) as indicated.
- Change from baseline in tumor markers (CEA, CA19-9)
- Change from baseline in CA125 (as a marker of inflammation)
- Changes from baseline in:
 - Clinician Global Clinical Assessment
 - Activities of daily living
 - Symptom rating
 - Quality of life (QCQ-C30)
 - Pain scale
 - ECOG

- Additional exploratory efficacy outcomes may be analyzed if feasible and will be defined in the CSR

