11.1 Safety Outcomes

11.1.1 Subject disposition

Subject disposition will be recorded at the EOS visit (120 days after the last implant) or at time of patient death or withdrawal, whichever occurs first.

Reasons why surviving patients received < 4 implants will be summarized. These reasons can include patient request (voluntary withdrawal), AE, protocol violation, request of Investigator or Regulatory Authority, request of Sponsor, lost to follow-up or other. One reason will be specified per patient.

Dates of Screening, date of the first scan showing disease progression after completion of prior treatment and the date of each implant will be listed.

Number and percentage of patients receiving 1, 2, 3 or 4 implants will be summarized. For all patients who received at least one implant, the number of days on study after each implantation will be summarized.

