Listings will include onset and resolution dates, study day in relationship to both first implant and most recent implant, duration (days), whether or not serious criteria apply, severity (mild, moderate, severe, life-threatening / disabling, death), action taken (none, discontinued), whether or not treatment was required, outcome (recovered, not resolved, residual effects, unknown, fatal) and relationship to study treatment (not related, remotely related, possibly related, probably related). Study day of onset in relationship to the first / most recent implantation will be calculated by subtracting the date of first / most recent implant from the AE onset date. AE duration will be calculated by subtracting AE onset date from AE resolution date. AEs that resolve on the same day will have duration = "< 1 day." Duration will not be calculated for AEs with missing or partial onset or resolution dates.

A summary of TEAEs will be provided, including incidence, severity and relationship to study treatment (implantation). TEAEs will be reported overall, as well as by SOC and PT. A summary of the most frequently reported TEAEs will also be provided, with "most frequently" defined as

occurring in at least 10% of all subjects. All TEAE summaries will be done over all implantations, as well as by implantation number.

Serious adverse events (SAEs) will also be summarized. SAEs and AEs that resulted in study discontinuation (as previously defined) will be listed separately.

Missing severity will be considered severe and missing relationship will be considered “probably related.” If the same TEAE is experienced more than once by a given subject, the TEAE will be counted only once for that subject. For summaries by severity, only the most severe TEAE per subject for each SOC and for each PT within SOCs will be tabulated. Similarly, for summaries by relationship to study treatment, only the most related TEAEs will be tabulated.

Deaths will be summarized separately, showing incidence of death overall, cancer-related death and cancer-related death by implantation number.

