16.2 Tables

Table #	Tables
14.1.1.1	Completion / withdrawal
14.1.1.2.1	Subject disposition, 1 implant
14.1.1.2.2	Subject disposition, 2 implants
14.1.1.2.3	Subject disposition, 3 implants
14.1.1.2.4	Subject disposition, 4 implants
14.1.2.1	Baseline characteristics
14.1.2.2	Contraception methods
14.1.2.3.1	Presenting oncology diagnosis
14.1.2.3.2	Previous oncology diagnosis
14.1.3	Con meds by drug class and preferred name
14.1.4	Number of Implantations and number of macrobeads implanted
14.2.1.1	Global Clinical Assessment
14.2.1.2	Activities of Daily Living
14.2.1.3	Quality of Life Scale (imputed)
14.2.1.3X	Quality of Life Scale (not imputed)
14.2.1.4.1	Pain Scale Assessment, Pain Level
14.2.1.4.2	Pain Location
14.2.1.5	ECOG
14.2.2.1	Tumor markers
14.2.2.2	Cytokines
14.2.3	Tumor size and state
14.2.4	Overall survival (from the most recent radiological scan showing evident disease progression to death)
14.2.5	Time from first implantation to death
14.2.6	Time from diagnosis of Stage IV disease to death
14.3.1.1.1	AE summary
14.3.1.1.2	Death summary
14.3.1.2	Treatment-emergent AEs by SOC
14.3.1.3.1	Treatment-emergent AEs by SOC and preferred term
14.3.1.3.2	Treatment-emergent AEs by severity
14.3.1.3.3	Treatment-emergent AEs by relationship
14.3.1.6	Treatment-emergent frequently reported ($\geq 2\%$ in all patients combined) AEs
14.3.2	Treatment-emergent SAEs by severity
14.3.4.1.1	Serum Chemistry Observed & Changes

Table #	Tables
14.3.4.1.2	Serum Chemistry, out of range flags
14.3.4.1.3	Serum Chemistry, Shift Table
14.3.4.1.4	Serum Chemistry Toxicity Grades
14.3.4.2.1	Hematology Observed & Changes
14.3.4.2.2	Hematology, out of range flag
14.3.4.2.3	Hematology, Shift Table
14.3.4.2.4	Hematology Toxicity Grades
14.3.5.1	Physical exam
14.3.6.1	Vital signs
14.3.6.2	Vital signs from diary
14.3.7	ECG

Mortality Figures	
16.2.6.4.1	Overall survival (from the most recent radiological scan showing progression)
16.2.6.5.1.1	Time from first implantation to death
16.2.6.5.1.2	Time from diagnosis of Stage IV disease to death

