16.3 Figures

Figure #	Figure
14.2.1.1.1.1	Progression-Free Survival: any death
14.2.1.1.1.2	Progression-Free Survival: cancer-related death
14.2.1.1.X	Progression-Free Survival by Stratifier X
14.2.1.2.1	Overall Survival
14.2.1.2.X	Overall Survival by Stratifier X
14.2.1.3.1	Radiographically-evident PFS
14.2.1.3.X	Radiographically-evident PFS by Stratifier X
14.2.2.1.1	CA125, colorectal
14.2.2.1.2	CA125, pancreatic
14.2.2.2.1	Tumor markers, CA 19-9, colorectal
14.2.2.2.2	Tumor markers, CA 19-9, colorectal
14.2.2.3.1	Tumor markers, CEA, colorectal
14.2.2.3.2	Tumor markers, CEA, pancreatic
14.2.3.1.1	Chemistry, C-reactive protein, colorectal
14.2.3.1.2	Chemistry, C-reactive protein, pancreatic
14.2.4.1.1	Hematology, Sedimentation rate, colorectal
14.2.4.1.2	Hematology, Sedimentation rate, pancreatic

End of Analysis Plan

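### SAP 10.2 plans survival comparisons by implantation number without a grouping rule or a stated clock; if total implants received is the grouping, the comparison has immortal-time bias (minor, exploratory)

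*SAP*

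**What the plan says.** The plan for this comparison is one bullet in SAP 10.2: "Survival comparisons by implantation number will be performed, if feasible". It gives no grouping rule, model or handling of the time before later implants.

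- **Clock.** SAP 6.4.1 assigns an origin to each of three time-to-death analyses (progression scan, first implantation, Stage IV diagnosis); this comparison is not one of them. The Kaplan-Meier bullet in SAP 10.2 measures time from implantation without saying which one.
- **Access to later implants.** Protocol 4.1 and SAP 3.2 allow up to four implants at least three months apart. The decision paragraph after Protocol 5.1.9 makes the second implant depend on clearance after the Day 90 review; the third and fourth follow the same pattern.
- **Use of implant number elsewhere.** SAP 11.1.1 states: "Number and percentage of patients receiving 1, 2, 3 or 4 implants will be summarized". The table list has entries such as "Subject disposition, 2 implants". For adverse events, SAP 11.1.2 states: "All TEAE summaries will be done over all implantations, as well as by implantation number". It also summarises "cancer-related death and cancer-related death by implantation number".
- **Outputs.** No table or figure is named for this comparison. The nearest is the placeholder "Overall Survival by Stratifier X" in SAP 16.3.
- **Related text.** SAP 10 states: "There will be no formal hypothesis testing and no group comparisons are currently planned". Protocol Appendix 3, section 4, plans a sub-analysis of efficacy response after one to four implantations, also without a grouping rule.

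**The concern.** The most direct way to carry out the bullet is a Kaplan-Meier or Cox analysis with patients split into 1, 2, 3 and 4 implants, as in the disposition summaries. That split uses information from after the clock starts. A patient who dies at two months can only be in the one-implant group, and a four-implant patient has necessarily survived about nine months. All three clocks in SAP 6.4.1 start at or before the first implant, so all of them include this guaranteed time.

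The stake is interpretation. Repeat implantation is the core of the design, and SAP 3.2 says the trial is meant to supply estimates for planning later trials. An apparent survival gradient with implant number could be read as a reason to re-implant when it comes from the grouping alone. Labelling the analysis exploratory deals with error control; it does not remove a bias whose direction is built in.

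**Working it through.** The plan has no figure to reproduce: SAP 3.4 rests the sample size on practical grounds, and neither document gives a survival or re-implantation rate. The check asks what the comparison shows when implants have no effect.

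**Inputs from the documents.** Spacing of three months (Protocol 4.1, SAP 3.2), or 98 days in the SAP 6.4.4 visit windows. Group sizes 20 and 10 (SAP 3.2), or 40 pancreatic and 74 − 40 = 34 colorectal (Protocol Appendix 3, section 9).

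**Assumptions.** Exponential survival from implant 1, true median 6 months (range 4–9), 50–70% of survivors re-implanted at each opportunity, no censoring, two-sided 5% tests.

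**1. Medians by total implants (6 months, 50%).**
- Survival to 3 months: 2^(−3/6) = 0.7071.
- One-implant group: deaths before 3 months, 0.2929, plus survivors not re-implanted, 0.5 × 0.7071 = 0.3536; total 0.6464.
- Its median is where 0.6464/2 = 0.3232 have died. Early deaths supply 0.2929, leaving 0.0303 = 0.5 × (0.7071 − S(t)). So S(t) = 0.6464 and t = 6 × log2(1/0.6464) = **3.8 months**.
- A constant hazard has no memory, so the two- and three-implant groups add 3 and 6 months: **6.8** and **9.8**.
- The four-implant group has a full median after month 9: 9 + 6 = **15.0**.

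**2. Other inputs.**
- At 70% re-implanted, the one-implant group is 0.2929 + 0.3 × 0.7071 = 0.5050. Half is 0.2525, reached before month 3, so S(t) = 0.7475 and t = 2.5. Medians: 2.5/5.5/8.5/15.0.
- With 98-day spacing, a 180-day median and 50%: S(98) = 2^(−98/180) = 0.6857, and the one-implant group is 0.3143 + 0.3428 = 0.6572. With p = 0.5 the same algebra gives S(t) = 0.6572, so t = 109 days. Medians: 109, 109 + 98 = 207, 109 + 196 = 305, and 294 + 180 = 474 days.
- Over true medians of 4–9 months (3-month spacing, 50–70%): 2.0–6.6 / 5.0–9.6 / 8.0–12.6 / 13.0–18.0 months.

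**3. Estimates and tests (null simulation, 2,000 trials per setting).**

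| Quantity, no true effect | Total implants, fixed | Cumulative implants, time-dependent |
|---|---|---|
| Hazard ratio per implant, n = 20–40, 50–70% re-implanted | 0.52–0.79 | 0.99–1.06 |
| Hazard ratio per implant, n = 10, 50–70% re-implanted | 0.45–0.78 | 0.91–1.09 |
| Hazard ratio per implant, n = 20–40, 90% re-implanted (400 trials) | about 0.37–0.58 | about 0.83–0.97 |

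A fixed log-rank test of one against two or more implants (180-day median, 98-day spacing, 50%) is falsely significant in 23% of trials at n = 20, 33% at n = 34 and 39% at n = 40. The score test in the time-dependent model errs in 5–8% of trials at n = 20–40 and 6–9% at n = 10 (50–70% re-implanted).

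**4. Clock restarted at each implant.** With one common hazard the median is 6.0 months from every implant, so there is no gradient. If prognosis varies (gamma frailty, variance v, h = ln2/6), the median remaining survival of those alive at t is (2^v − 1)(1 + v·h·t)/(v·h). At t = 0, 3, 6, 9 months this gives 7.2/8.4/9.7/10.9 for v = 0.5 and 8.7/11.7/14.7/17.7 for v = 1.0. Clearance favouring fitter patients steepens it. The immortal time goes; selection stays.

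**5. Limit of the time-dependent model.** With frailty plus clearance favouring fitter patients (v = 0.5 or 1.0, two assumed strengths, n = 20–40), its null hazard ratio is still 0.52–0.79 per implant, against 0.39–0.57 for the fixed grouping.

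**The case against.** The strongest reply is that the bullet need not mean total implants. In the adverse-event sentence of SAP 11.1.2, by implantation number most naturally means the period after each implant, and the death summary there fits either sense, because a patient's last implant number equals the total received. The disposition text that groups by totals does not use the phrase. This stands: the immortal-time bias is conditional on a reading the text does not settle. The other reading still needs its clock stated, and it still compares selected patients.

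The analysis is also to be done only if feasible, all testing is labelled exploratory, and every survival and re-implantation rate above is assumed. That bears on severity and on the exact figures, not on the direction of the bias.

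Three stronger readings are tempting and not supported.
- A reader might infer that SAP 10 and SAP 10.2 contradict each other. The SAP 10 sentence follows one on stratification by cancer type. SAP 3.2 disclaims comparisons between the two cancer types, and Protocol Appendix 3, section 1, says the same. Group there most naturally means cancer type, so this is wording to clarify.
- A reader might infer that no usable time origin exists. SAP 6.4.1 does define first implantation as one; what is missing is which origin applies here.
- A reader might treat 98 days as a firm minimum spacing. The same SAP table labels days 83–97 as Day 90 if before the next implant, which allows for an implant inside that window. About three months is the safer description.

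**Conclusion.** The point holds as a conditional and minor one. SAP 10.2 leaves both the grouping and the clock open. Under fixed grouping by total implants, a null treatment gives medians of 3.8/6.8/9.8/15.0 months (assumed 6-month median, 50% re-implanted, three-month spacing) and a hazard ratio per implant of 0.52–0.79 at n = 20–40 over the 50–70% settings. Under a clock restarted at each implant there is no immortal time, and any gradient comes from selection.

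A reader might go further and conclude that the trial's survival results are biased. They are not affected: the primary outcome and the listed secondary time-to-death outcomes do not use implant number. The sizes rest on exponential survival, the assumed rates and no censoring; the direction follows from the rule that later implants require survival and clearance.

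**What to change.** Replace the SAP 10.2 bullet with:

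> The association of implant number with survival will be described by cancer type, from first implantation, using a Cox model with cumulative implants received as a time-dependent covariate based on actual implant dates. Total implants received will not be used as a fixed survival grouping. Results are descriptive, because clearance for re-implantation selects fitter patients.

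In SAP 10, state that the sentence on group comparisons refers to cancer types, if that is what is meant.

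**Cost.** SAP wording and a start-stop dataset. The dates are already available: SAP 11.1.1 provides for the progression-scan date "and the date of each implant will be listed". Intervals will be wider and small-sample error modestly inflated. The model may not be estimable in a 10-patient group or when nearly all survivors are re-implanted; if every survivor is re-implanted exactly on schedule, implant number and elapsed time cannot be separated at all. With 90% re-implanted the estimate drifts below 1 without any effect. Selection by clearance remains, so the descriptive caveat must stay with the result.

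Deleting the bullet is possible, but it must then be reconciled with the sub-analysis by number of implantations in Protocol Appendix 3, section 4, and any difference explained in the CSR, as SAP 1 requires.

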11 SAFETY ANALYSES

Safety parameters will be listed and summarized for all implanted subjects, stratified by cancer type. Safety analyses will involve the examination of incidence and reasons for discontinuation; incidence of AEs and their relationship to study treatment; changes in clinical laboratory results, vital signs, weight, 12-lead ECG parameters, physical examination findings, murine antigens skin test and murine leukemia virus.

11.1 Safety Outcomes

11.1.1 Subject disposition

Subject disposition will be recorded at the EOS visit (120 days after the last implant) or at time of patient death or withdrawal, whichever occurs first.

Reasons why surviving patients received < 4 implants will be summarized. These reasons can include patient request (voluntary withdrawal), AE, protocol violation, request of Investigator or Regulatory Authority, request of Sponsor, lost to follow-up or other. One reason will be specified per patient.

Dates of Screening, date of the first scan showing disease progression after completion of prior treatment and the date of each implant will be listed.

Number and percentage of patients receiving 1, 2, 3 or 4 implants will be summarized. For all patients who received at least one implant, the number of days on study after each implantation will be summarized.

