5.9 Rescue Program

During the time period that a subject is participating in this clinical study, the need may arise for additional oncologic therapy. If an alternative or additional therapy other than the macrobeads becomes indicated, because of disease progression, this type of therapy would be considered Rescue Therapy. This would include, for example, chemotherapy, radiation, surgery, or a different experimental protocol. This rescue program would be instituted and would not require the subject to be discontinued from the RENCA macrobead protocol. While undergoing these treatments, the subject will continue to be closely monitored for disease status as well as toxicity, as specified in this protocol. Should the clinical situation develop, the principal investigator and subject, with appropriate consultant input, could restart treatment with the macrobeads. A treatment "holiday" of at least three weeks (for chemotherapy) and four weeks (for radiation) would be required before commencing with this phase II protocol.

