End of Study	When all patients have died or have been lost to follow-up, whichever occurs first
Enrolled Patients	Eligible patients who have signed an Informed Consent Form (ICF)
Sponsor	The Rogosin Institute
Time of origin (T_0)	Date of the first scan showing disease progression after completion of prior treatment. Scan must be prior to first implant. Used for mortality analyses only.
Treated Population	Patients who received at least one implant
Treatment-Emergent Adverse Event (TEAE)	An adverse event which occurred during or after the first implantation and up to 120 days after the last implantation

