3.3.2 Safety

Safety outcomes will include:

- Reason for study discontinuation (coming off protocol).
- Incidence of adverse events (AEs).
- Changes from baseline in physical examination parameters, including weight, vital signs, and electrocardiogram (ECG).

- Changes from baseline in laboratory parameters (see [Section 11.1.3](#)).
- Changes from baseline in murine antigens skin test.
- Changes from baseline in status of murine leukemia virus as detected by polymerase chain reaction (PCR).

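### SAP 11.1.1 limits the summary of reasons for fewer than four implants to surviving patients, without dating survival and against SAP 11, so some patients who stop and then die have no reported reason

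*SAP*

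**What the plan says.** The first safety outcome in SAP 3.3.2 is "Reason for study discontinuation (coming off protocol"), and Protocol 3.1.2 lists the same outcome for the colorectal group. Neither restricts it to survivors. SAP 11 sets the population: "Safety parameters will be listed and summarized for all implanted subjects, stratified by cancer type". Its next sentence places the incidence of and reasons for discontinuation within the safety analyses. SAP 5 likewise puts everyone with at least one implant into all safety evaluations.

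SAP 11.1.1 is the section that carries this out. On timing it says: "Subject disposition will be recorded at the EOS visit (120 days after the last implant) or at time of patient death or withdrawal, whichever occurs", in other words at the earliest of the three. On the reasons it says: "Reasons why surviving patients received < 4 implants will be summarized". The list is: "These reasons can include patient request (voluntary withdrawal), AE, protocol violation, request of Investigator or Regulatory Authority, request of Sponsor, lost to follow-up or other". Finally: "One reason will be specified per patient".

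**The concern.** The rule that produces the table is narrower than the outcome it serves, and the word that narrows it has no date attached. Two programmers could build different tables from the same data.

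The patients at risk of being dropped are those who stop implants and die soon afterwards. Under SAP 3.2 the trial's main purpose is to estimate parameters for planning later studies. For a regimen of up to four implants, how many patients cannot go on to the next implant, and why, is one of those parameters.

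The reason list adds to the problem. The review before each implant (the decision-to-proceed paragraphs in Protocol 5.1) can end in non-clearance. Progression prompts a documented discussion of other therapy (Protocol 5.8). Neither is a named category, so both end up under the open category or under a request by the investigator, where they cannot be told apart.

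**Working it through.** The documents state no figure on this point, so there is none to reproduce. The check compares the texts and then illustrates the size.

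**Who is in the table, by the date at which survival is judged**

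- *When disposition is recorded.* This is the earliest of the 120-day visit, death and withdrawal. A patient who formally withdraws and dies later is alive at recording and can be included. A patient who misses the next implant, does not formally withdraw and dies before the 120-day visit is recorded at death and is excluded.
- *At a later analysis date.* Everyone who has died by then is excluded, whatever the earlier reason for stopping.
- *At End of Study as given in the SAP List of Definitions.* That is "When all patients have died or have been lost to follow-up, whichever occurs first", so only patients lost to follow-up could remain. SAP 3.2 has a different study end, 120 days after the last active subject's last implantation.

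**Whether another output supplies the missing reason**

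- The death summary in SAP 11.1.2 gives incidence, cancer-relatedness and implantation number, but not why implants stopped.
- Adverse events leading to discontinuation are listed without a survivor limit, but that listing covers adverse events only.
- Tables 14.1.1.1 and 14.1.1.2.1 to 14.1.1.2.4 and Listing 16.2.1.1 have titles but no stated content.

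None is stated to give the reason implants stopped for a patient who later died.

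**Illustration of size**

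Assumptions: exponential survival from first implant, medians *m* of 3, 6, 9 and 12 months, 30.4375 days per month, and the same hazard whether or not a patient is re-implanted. The Day 90 review and the 120-day visit come from the plan; the medians do not.

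For a patient alive on day *a*, the probability of dying by day *b* is 1 − 0.5^((b − a)/(30.4375 × m)). For example, with m = 3, a = 90 and b = 120, this is 1 − 0.5^(30/91.31) = 20.4%.

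| Median (months) | Dies Day 90 to 120 | Dead by 12 months (Day 365), alive at Day 90 | Dead by 24 months (Day 730), alive at Day 90 |
|---|---|---|---|
| 3 | 20.4% | 87.6% | 99.2% |
| 6 | 10.8% | 64.8% | 91.2% |
| 9 | 7.3% | 50.1% | 80.2% |
| 12 | 5.5% | 40.7% | 70.3% |

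The first column applies to patients alive at Day 90, not re-implanted and not formally withdrawn. It is the loss under the most favourable reading. If the decision to stop came at eight weeks (Day 56), the earliest point at which Protocol 5.8 prompts the progression discussion, the interval is 64 days and the loss is about 38, 22, 15 and 11%.

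**The case against.** The strongest reply is that *surviving* only means not already accounted for by death. Deaths are summarised separately, SAP 11 already requires all implanted subjects, and the numbers receiving 1, 2, 3 or 4 implants are tabulated for everyone. On that view one word needs tidying. Much of this stands: formal withdrawals who die later can be included, and the distribution of implant counts is not lost. It does not cover the patient who stops without withdrawing and dies before the 120-day visit, and it does not date the word.

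Three stronger readings are tempting, and the documents do not support them.

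- *Every death within 120 days of the last implant removes a reason for stopping.* With medians of 3, 4, 6 and 8 months that would be 60, 49, 37 and 29%, from 1 − 0.5^(3.94/m). This counts deaths before any stopping decision, where death itself is usually why no further implant was given. It also counts recipients of four implants, who are not in this table, and formal withdrawals.
- *The share stopping for adverse events is biased downward.* This is not shown. If early deaths mainly follow progression, the adverse-event share among survivors would rise.
- *Progression and rescue therapy cannot be recorded as reasons.* The list is introduced as examples and ends with an open category, so they can be recorded but not distinguished. Rescue therapy is also not a discontinuation: Protocol 5.9 says it "would not require the subject to be discontinued from the RENCA macrobead protocol".

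The CRF was not among the documents. It may already hold finer codes, but the SAP does not say so.

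**Conclusion.** The point holds as a conflict between SAP 11.1.1 and SAP 11, SAP 3.3.2 and Protocol 3.1.2, made worse by an undated condition. Patients who miss the next implant, do not formally withdraw and die before the 120-day visit are left out on every reading, and a later survival date leaves out more. On the assumed medians the loss runs from about 6 to 20% of the group at risk between Day 90 and Day 120, and from about 41 to 88% of those alive at Day 90 if survival is judged at 12 months. These ranges rest on assumed exponential survival and show scale only. The direction of any bias is open.

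This is a defect in one descriptive safety table of an exploratory study. It does not affect the primary analysis or the sample size.

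**What to change.** Delete *surviving* in SAP 11.1.1 and replace the sentence with wording such as: for every patient in the Treated Population with fewer than four implants, the reason the next implant was not given will be summarised by implant interval (after Implants 1, 2 and 3), with all patients who received the preceding implant as denominator.

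- Show as separate categories: death before the next implant, disease progression, new or rescue therapy, and not cleared for implantation, alongside the existing ones.
- Report later death separately, so that it does not replace the reason for stopping.
- Report fewer than four implants and coming off protocol as two distinct items, because rescue therapy can explain the first without implying the second.

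The cost is SAP wording, a code list and one table. The reviews before each implant are already required by Protocol 5.1 and 7.2, so the information should exist in source. The downside is some retrospective coding for patients already treated. No treatment rule changes.
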